- Symptomatic vertebral stenosis resulting from presumed atheromatous disease.
- Severity of stenosis at least 50% as determined by MRA or CTA or intra-arterial angiography.
- Symptoms of TIA or non-disabling stroke within the last three months.
- Patient able to provide written informed consent, be willing to be randomised to either treatment, and be willing to participate in follow-up.
- If randomised to stenting, this can be performed within two weeks after randomization.

Exclusion Criteria:

- Patients unwilling or unable to give informed consent.
- Patients unwilling to accept randomisation to either treatment arm.
- Vertebral stenosis caused by acute dissection as this has a different natural history and usually spontaneously improves.
- Patients in whom vertebral stenting is felt to be technically not feasible e.g. access problems.
- Previous stenting in the randomised artery.
- Pregnant and lactating women.

RANDOMISATION

Randomisation will be stratified by the site of vertebral stenosis.

Stent Register

A log of stented patients with symptomatic vertebral stenosis not randomised to the trial will be kept at participating centres. This will allow us to determine whether a significant proportion of patients receiving stenting were not entered into the study and had open treatment. This will help assess any overall bias in the study.

Consent

Written informed consent will be obtained from all patients. All patients will be provided with a written information sheet explaining the study.

PATIENT ASSESSMENT SCHEDULE

Patient assessments will take place at the following time points;

- Hospital Visit 1 Baseline Visit
- Hospital Visit 2 At randomisation (if allocated to stenting)
- Hospital Visit 3 at One Month post randomisation
- Telephone Follow-up Call at 6 months
- Hospital Visit 4 at One Year
- Telephone Follow-up Call Yearly from year 2 onward until study end

Follow-up will range from 2 years for the last recruited patients to up to about 8 years for first patients recruited.

At each hospital visit neurological assessment and recording of TIA, stroke and other complications will be performed. Full cardiovascular risk factor assessment will be made.

Patient follow-up post procedure and at one month and one year will be performed by a designated neurologist or stroke physician. All other follow-up will be performed using telephone follow-up.

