For UK patients only, health and social care contacts during the first two years will be collected prospectively using patient diaries. Hospital contacts will also be obtained from patient records. The EQ-5D (www.euroqol.org) will be administered at each follow-up.

To help prevent the loss of participants to follow-up and accurately measure study outcomes, cases in the UK are tracked using the NHS Information Centre Medical Research Information Service. This will include providing relevant information to the Chief Investigator when the following occur during follow up:

- A participant dies
- A participants Primary Care Trust (PCT) changes

Where contact with a subject has been lost and a notification of PCT change has been received, the Chief Investigator will contact the PCT to request details of the participants new General Practitioner (GP). Subsequently the Chief Investigator will then contact the identified GP to request the contact detail of the participant or that his contact details are passed onto the participant.

All end-points or serious adverse events will be reviewed by an independent adjudication committee.

Imaging of the Vertebral Arteries

Prior to randomisation the likely presence of a vertebral stenosis must be demonstrated on imaging. The following imaging modalities are acceptable:

- Magnetic resonance angiography (preferably contrast enhanced)
- Contrast enhanced CT angiography
- Intra-arterial digital subtraction angiography

In the interventional arm digital subtraction angiography will be performed prior to angioplasty/stenting. Stenosis will be measured by a NASCET type method. The residual lumen will be divided by vessel diameter at a point distal to the stenosis where normal vessel calibre has been restored.

Copies of all angiographic will be collected centrally. Information on collateral supply will be collected.

Follow-Up Imaging

Follow-up imaging will be performed in both the interventional and medical arms.

All patients will be followed up with either MRA or CTA at 1 year. Magnetic resonance angiography or CT angiography will be performed to check for vessel patency although it is recognised that in patients with stents these modalities are unlikely to give good quality images of the degree of stenosis.

In all patients with recurrent symptoms (TIA or stroke) repeat brain imaging and vertebral imaging will be performed.

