Where performed results from intra-arterial digital subtraction angiography will be collected although it is considered that it is not ethical to perform this routinely unless clinically indicated.

Restenosis will be defined as stenosis >50% in the treated artery.

Medical Treatment

All patients will receive best medical treatment including antiplatelet therapy or anticoagulation (when appropriate) and control of medical risk factors including hypertension, smoking and hyperlipidaemia. Use of antiplatelet agents will be recorded for both arms.

Angioplasty/Stenting Protocol

Angioplasty/Stenting should be performed as soon as possible, and certainly within 2 weeks, after randomisation using percutaneous transluminal interventional techniques from the femoral or brachial artery. It is expected that stenting will be the preferred procedure for proximal vertebral stenosis, but for distal stenosis the choice of angioplasty alone or stenting will be at the discretion of the interventional radiologist.

The recommended antiplatelet therapy during the procedure is Clopidogrel and Aspirin. If the patient is not on Clopidogrel at the time of the procedure they should be loaded with 300-600mgs at least twelve hours pre-procedure. Heparin should be given during the procedure. It is recommended that Clopidogrel and Aspirin is continued for at least one month post procedure after which standard antiplatelet therapy for stroke prevention should be used.

Experience Required by Centres

Each centre must have a neurologist or physician with an interest in stroke who will see patients prior to randomisation and for follow-up. Vertebral stenting/angioplasty will be carried out by a designated consultant interventionist with experience in cerebral angioplasty/stenting. Vertebral stenting is a relatively new procedure and therefore most centres will not have extensive experience. Interventionists will be expected to have performed a minimum of 50 stenting procedures of which at least 10 will be on cerebral vessels. Centres with less than this level of experience will join for a probationary period and when they will be proctored by an experienced interventionist until they have performed 10 procedures. Proctoring will be co-ordinated by experienced interventional consultant neuroradiologists.

OUTCOME EVENTS

- A. Primary End Point
 - Fatal or non-fatal stroke in any arterial territory (including periprocedural stroke) during trial follow up
- B. Secondary End Points

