 - Fatal or non-fatal stroke in any arterial territory (including periprocedural stroke) at three months post-randomisation
 - Posterior circulation stroke (including periprocedural stroke) during follow-up
 - Periprocedural stroke or death (within 30 days of procedure)
 - Posterior circulation stroke and TIA during follow-up
 - Any disabling stroke (defined by a Rankin >=3) during follow-up
 - Death of any cause during follow-up
 - Restenosis in treated artery during follow-up
 - NHS and personal social services costs

- Quality-adjusted life years
- Within-trial and long-run incremental cost-effectiveness

Periprocedural is defined as 30 days post-procedure.

SAMPLE SIZE CALCULATIONS AND STATISTICAL ANALYSIS

A reasonable estimate from currently available evidence is that the stroke risk in the medically treated arm will be of the order of 12% in year 1, 6% in years 2, and 4% in years 3, i.e. 24% over a three year period. A reasonable, but perhaps conservative estimate (in view of the magnitude of benefit in the carotid endarterectomy trails), estimate of the risk reduction in the stented arm is 45% (including periprocedural rate).

Sample size calculations have been prepared by the Stroke Research Network Statistical support Unit ([name]).

Calculations assume a significance level of 5% and power of 80%. Calculations are performed for a chi-squared test comparing two proportions. Calculations were performed using nQuery Advisor software version 6.02. The table provides the number of patients required in each treatment group. The sample sizes required correspond to three assumed average event rates and a variety of assumed treatment effects expressed as hazard ratios.

Table: Numbers of participants required per group to achieve 80% power (5% significance level) to detect the specified hazard ratio (treatment effect) assuming the specified event rate in the control group.

Hazard ratio	Control group event rate		
	20%	24%	28%
0.65	521	433	370
0.60	387	321	274
0.55	296	245	210
0.50	232	192	164
0.45	185	154	131
0.40	150	125	107

On the basis of these calculations, the number of patients needed is estimated to be 245 per group (490 in total). We have increased the number by 10% to take account any cross–overs or lost to follow-up for reasons other than stroke to give us a sample size of **540**.

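### Restenosis is defined only as stenosis above 50% in the treated artery, with no requirement that the artery was first opened, so residual stenosis after a completed procedure is scored as restenosis

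*Protocol*

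**What the plan says.** All references are to the protocol; the SAP is not at hand.

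- **Follow-Up Imaging** gives the rule: "Restenosis will be defined as stenosis >50% in the treated artery". No other condition is attached.
- **Outcome Events, Secondary End Points** lists the end point that uses it: "Restenosis in treated artery during follow-up".
- **Inclusion Criteria** set the entry level: "Severity of stenosis at least 50% as determined by MRA or CTA or intra-arterial angiography".
- **Imaging of the Vertebral Arteries** places procedural angiography before the intervention: "In the interventional arm digital subtraction angiography will be performed prior to angioplasty/stenting". No end-of-procedure measurement is stated.
- **Follow-Up Imaging** schedules one later vessel image ("All patients will be followed up with either MRA or CTA at 1 year"), with further vertebral imaging if symptoms recur.
- **Angioplasty/Stenting Protocol** expects stenting for proximal lesions, but "for distal stenosis the choice of angioplasty alone or stenting will be at the discretion of the interventional radiologist".

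Technical success, a maximum residual stenosis, a post-procedure reference value and a required change from it are not defined anywhere in the protocol.

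**The concern.** Restenosis means that an opened artery has narrowed again. The written rule looks only at the level at follow-up. Because that level is also the entry level, an artery that the procedure improved too little to cross 50% already meets the definition before any follow-up time has passed. The end point then mixes two things: an initial result that was not good enough, and later loss of a good result.

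The mixture matters most where initial results vary. For distal lesions the operator may choose angioplasty alone, and Trial Design says that efficacy will be determined for extracranial and intracranial stenosis separately. If initial results differ by technique or site, and restenosis is tabulated by site, part of that difference would appear under the name of restenosis.

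The fault lies in the derivation rule. It would remain if every follow-up image were graded without error. It is therefore separate from the protocol's own caution that "in patients with stents these modalities are unlikely to give good quality images of the degree of stenosis".

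**Working it through.** The protocol states no figure that depends on this definition, so there is none to reproduce. The check has two parts.

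**1. Apply the rule to records.** Entry requires stenosis ≥50% and the end point requires >50%, so the cut-offs differ only at exactly 50%.

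| Entry | End of procedure | One year | Scored | Re-narrowed? |
|---|---|---|---|---|
| 75% | 15% | 60% | restenosis | yes |
| 75% | 55% (procedure completed) | 55% | restenosis | no |
| 70% | 70% (attempt abandoned) | 70% | restenosis only if this artery counts as treated | no |

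The records are constructed examples. The second row follows from the wording alone. The third depends on what makes an artery treated, which the protocol does not say.

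**2. Illustrate the size.** Let

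- f = share of treated arteries left above 50% at the end of the procedure. This is **assumed**: the documents give no value. Range shown: 2%, 5%, 10%.
- r = true restenosis among arteries opened to 50% or less. The two background rates in Previous Work in the Field serve as stand-ins: 10.4% (distal angioplasty) and 25.7% (proximal stenting).

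Assume that arteries left above 50% stay above 50%, that all treated arteries are imaged, and that grading is exact. Then

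recorded rate = f + (1 − f) × r, and the excess over r is f × (1 − r).

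| f | r = 10.4% | Excess | r = 25.7% | Excess |
|---|---|---|---|---|
| 2% | 0.02 + 0.98 × 0.104 = 12.2% | 1.8 points | 0.02 + 0.98 × 0.257 = 27.2% | 1.5 points |
| 5% | 0.05 + 0.95 × 0.104 = 14.9% | 4.5 points | 0.05 + 0.95 × 0.257 = 29.4% | 3.7 points |
| 10% | 0.10 + 0.90 × 0.104 = 19.4% | 9.0 points | 0.10 + 0.90 × 0.257 = 33.1% | 7.4 points |

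Under a definition that requires an opened artery, the rate among opened arteries would be r in every row.

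**The case against.** **The word implies prior opening, and end points are adjudicated.** Patient Assessment Schedule sends all end points to an independent committee, and its members may well apply the ordinary meaning of the word. But the only written criterion they have is the level above 50%, and an SAP or charter that follows the protocol literally inherits it. The protocol has not left the definition open for a later document; it has fixed one.

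**A plain level may be what was intended.** The protocol nowhere says that the end point measures durability; it describes follow-up imaging as a check of patency. Whether a treated artery is more than 50% narrowed at follow-up is a legitimate question, and conditioning on initial success answers a different one. This stands as a reason to keep failures visible in the report. It is not a reason to call them restenosis.

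**Failed procedures.** A reader might infer that every failed attempt is counted. The documents do not support that: the rule concerns the treated artery, the protocol does not say whether an abandoned attempt makes an artery treated, and patients in whom stenting is judged technically infeasible are excluded beforehand. Nor does the protocol say that the rule extends to medically managed arteries, although "Follow-up imaging will be performed in both the interventional and medical arms".

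**Comparison with the background rates.** A reader might also infer that the trial's rate would not be comparable with 25.7% and 10.4%. The protocol does not say how the cited review defined restenosis, so no mismatch can be asserted.

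**Importance.** This is one secondary end point among several, with no power statement attached. That is correct and limits the weight of the point.

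**Conclusion.** The point holds in a limited form. Read as written, the definition scores a completed procedure with residual stenosis above 50% as restenosis without any re-narrowing. That conclusion rests on the text alone. Abandoned attempts are affected only if such arteries are regarded as treated.

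The size is not known. Over the assumed 2% to 10% of arteries left above 50%, the recorded rate rises by 1.8 to 9.0 points when true restenosis is 10.4%, and by 1.5 to 7.4 points when it is 25.7%. These figures illustrate the mechanism and do not predict this trial. A reader might infer from the top of the range that the artefact could rival the quantity being measured. The documents give no residual-stenosis rate that would support this, and where stents open the artery well the effect would be small.

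One secondary end point is affected. The primary stroke end point and the sample size are not. The definition should be corrected because a stated rule misclassifies cases and the correction is cheap.

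**What to change.** In Follow-Up Imaging, replace the definition so that:

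1. Restenosis is stenosis above 50% at follow-up in an artery whose documented end-of-procedure residual stenosis was 50% or less.
2. Those arteries form the denominator.
3. Residual stenosis above 50% at the end of the procedure, and lesions not opened, are reported separately as technical failure, so that no treated patient disappears from the report.
4. The end-of-procedure stenosis is recorded from the procedural angiogram. This has to be stated: the protocol collects angiograms centrally but specifies angiography only before the procedure, so the value cannot be assumed to be in hand.

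Requiring an end-of-procedure value also makes clear that the definition applies only to arteries that underwent the procedure.

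The cost is a change to the definition, one extra data field and a slightly smaller denominator. The new rule still has no minimum change (49% to 51% would count) and does not improve image quality within stents. It removes only the confusion of residual stenosis with re-narrowing.

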We will also perform a pre-planned pooled analysis of the VIST data with the data from the only other currently recruiting trial of vertebral stenting of which we are aware, which is recruiting in the Netherlands, the Vertebral Artery Stenting Trial (VAST) (15).

This is recruiting 180 patients using a similar protocol to VIST. Therefore the combined sample size will be 720 (360 per treatment arm). With the same assumptions we made above (average event rate 24%, treatment effect is a hazard ratio of 0.55) this will provide us with power of **92%** at p=0.05.

As can be seen from the table, the required sample size depends strongly on the event rate and on the assumed treatment effect. In fact, for a given hazard ratio the critical factor is the total number of events observed (over both groups). For a hazard ratio of 0.55 this number is 88 events. Hence the trial steering committee will monitor the accumulating event rates and total number of events and discuss appropriate actions such as increasing the sample size or increasing the duration of follow-up. As the study moves towards the end of recruitment, we will also ask the DMC to review study progress and to carry out an analysis of conditional power. On this basis we will ask them to recommend whether or not the study should continue to its natural end or whether a modest increase in the sample size (Adaptive Design) might enable the study to identify an emerging treatment effect that is less than that predicted but still of clinical importance.

ASSESSMENT OF SAFETY

Safety measurements

All patients will have safety measurements taken throughout the study as all patients recruited are hospital inpatients.

Systolic, diastolic blood pressures and heart rate will be monitored regularly, standard 12-lead ECGs and blood samples taken for haematological and biochemical analysis will be performed as part of the clinical care of the patient. Any anomalies relating to these measurements will be investigated as part of the clinical care of the patient.

ADVERSE EVENTS

All adverse events must be followed up and fully and precisely documented in the patients medical notes.

Responsibilities of investigator

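### The protocol's yearly control-arm risks (12%, 6%, 4%) do not make the 24% three-year risk on which 245 per group rests: they give 22% added or 20.6% compounded

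*Protocol*

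**What the plan says.** All of this is in the protocol section on sample size calculations and statistical analysis, unless stated otherwise.

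- The control-arm stroke risk is put at "12% in year 1, 6% in years 2, and 4% in years 3, i.e. 24% over a three year period", introduced as an order-of-magnitude estimate.
- The treatment effect is an "estimate of the risk reduction in the stented arm is 45% (including periprocedural rate"), which the table uses as a hazard ratio of 0.55.
- On method: "Calculations are performed for a chi-squared test comparing two proportions", with 5% significance and 80% power.
- The table gives the number per group for control event rates of 20%, 24% and 28%. At a hazard ratio of 0.55 the entries are 296, 245 and 210.
- From the 24% column, "the number of patients needed is estimated to be 245 per group (490 in total"). A 10% addition for cross-overs and losses brings the total to 540.
- The pooled analysis with the Dutch trial (720 patients, 360 per arm) keeps the same assumptions, "average event rate 24%, treatment effect is a hazard ratio of 0.55", and states 92% power.
- On events: "For a hazard ratio of 0.55 this number is 88 events". The steering committee is to monitor event numbers and may extend recruitment or follow-up.

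Elsewhere, the outcome section defines the primary end point as stroke over the whole of trial follow-up. The assessment schedule puts that follow-up at 2 to about 8 years.

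**The concern.** The three yearly risks and the three-year total are offered as the same thing, and they are not. The total, not the yearly risks, enters the calculation. It picks the table column and so fixes 245, 490, 540 and the pooled 92%. The required number is sensitive to this input: in the protocol's own table, moving from 24% to 20% at a hazard ratio of 0.55 adds 51 patients per group (296 against 245), and the compounded figure lies close to the 20% column. A reader who takes the yearly risks at face value cannot recover the stated power on the stated three-year basis.

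**Working it through.** **Inputs from the protocol:** yearly risks 12%, 6% and 4%; stated total 24%; hazard ratio 0.55; 5% significance (taken as two-sided, which reproduces the table); 80% power; 245 per group; 360 per arm pooled.

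**1. Three-year control risk.**
- Added: 12 + 6 + 4 = 22%.
- Compounded, if each figure applies to patients still stroke-free: 1 − 0.88 × 0.94 × 0.96 = 20.6%.
- With a fourth year at 4%: 1 − 0.88 × 0.94 × 0.96 × 0.96 = 23.8% compounded, or 26% added.

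**2. Reproducing the protocol's 245.** Take the stented-arm risk from the hazard ratio: p2 = 1 − (1 − 0.24)^0.55 = 14.01%. Freedman's formula gives the events needed as (1.960 + 0.842)² × (1.55/0.45)² = 7.849 × 11.864 = 93.1. Per group, n = 93.1 / (0.24 + 0.1401) = 245. The same formula reproduces all 18 table cells to within about one patient. The plain chi-squared formula on the same two proportions gives 241 per group, and 80.7% power at 245. So 245 is right for a 24% control risk; the question is only where the 24% comes from.

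**3. Same method at the risks the yearly figures give.** p2 = 1 − (1 − p1)^0.55; events = n × (p1 + p2); power = Φ(√events × 0.45/1.55 − 1.960).

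| Control risk p1 | p2 | n per group for 80% | Events from 490 | Power at 245 per group (chi-squared) | Pooled power, 360 per arm (chi-squared) |
|---|---|---|---|---|---|
| 24% | 14.0% | 245 | 93 | 80.0% (80.7%) | 92.5% (92.9%) |
| 22% | 12.8% | 268 | 85 | 76.4% (77.0%) | 90.1% (90.6%) |
| 20.6% | 11.9% | 287 | 80 | 73.6% (74.2%) | 88.1% (88.6%) |

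Both corrected event counts fall short of the protocol's 88. That 88 is itself Schoenfeld's number, 4 × 7.849 / (ln 0.55)² = 87.8, whereas the table follows Freedman's 93. On Schoenfeld's formula the power at 245 per group is 78.8% (22%) or 76.0% (20.6%), but that formula does not reproduce the table: it gives 232 rather than 245.

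**4. The 10% addition.** If all 540 (270 per group) were evaluable and none crossed over, three-year power would be 80.3% at 22% and 77.6% at 20.6%. The addition is reserved for cross-overs and losses, so it cannot also cover this gap.

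**5. Power over the planned follow-up.** The accrual pattern is not given, so this is an assumption with a range. Let 4% a year continue after year 3, compound the yearly risks, apply the hazard ratio of 0.55 throughout, and take 490 evaluable patients.
- Follow-up spread evenly over 2 to 6 years: average control risk 23.7%, about 92 events, power about 79%.
- Follow-up spread evenly over 2 to 8 years: average control risk 26.6%, about 104 events, power about 84%.

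**The case against.** The strongest reply is that the slip may lie in a yearly risk, not in the total. The yearly figures appear once, in a sentence with visible typing faults, while the 24% is used consistently in that sentence, as the middle table column and in the pooled calculation. One wrong digit would explain it: 12 + 6 + 6 and 12 + 8 + 4 both make 24. In that case 245, 490, 540 and 92% stand. This objection holds: the document cannot show which figure is wrong, so one cannot insist that 24% be replaced by 20.6% or 22%. It works only if the risks are meant to add, since 12%, 6% and 6% compound to 22.2%.

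The second reply is that the 80% is attached to an average event rate of 24%, not to a three-year analysis, and that the primary end point counts strokes over the whole of follow-up. This also holds. A reader might infer from the table in the working that the trial is underpowered, or that it needs 268 to 287 per group. The documents do not support that: step 5 gives about 79% to 84% with the planned 490 evaluable patients.

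The third reply is that the protocol already acknowledges its sensitivity to the event rate, brackets 20% to 28% in the table, has events monitored and asks for a conditional-power review. These are real safeguards, and they leave no need for a new event-based closing rule. They guard against observed rates departing from the assumption, however; they do not make the stated assumption agree with itself. Nor does the order-of-magnitude wording, because the 24% is presented as the equivalent of the yearly figures.

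**Conclusion.** The mismatch is certain: on neither reading do the stated yearly risks make 24% over three years. Its size is moderate and conditional. If the yearly risks are right, the stated three-year basis carries about 76% or 74% power instead of 80%, about 85 or 80 events instead of 93, and pooled power of about 90% or 88% instead of 92%. These figures assume a hazard ratio of 0.55, a two-sided 5% level and the formula that reproduces the table. What is not established is that the 24% is the wrong figure, or that the trial as planned lacks power over its actual follow-up. The point concerns the stated justification for the sample size, not the sample size itself. Severity: should-fix.

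**What to change.** Reconcile the yearly risks with the 24%, in one of three ways.

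1. If a yearly risk is misprinted, correct it so that the total is 24%, and say whether the yearly risks add or compound.
2. If the yearly risks stand and three years is the intended basis, restate the three-year control risk (22% or 20.6%), the power for 490 evaluable patients (about 74–76%) and the pooled power (about 88–90%).
3. If the yearly risks stand and 24% is to be kept, state the follow-up it refers to: about four years with 4% a year continuing (23.8% compounded), which is in line with the planned 2 to about 8 years.

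The cost is protocol wording and, under the second option, a less favourable stated power. No extra patients are needed, and no test or analysis changes.

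### The 88-event monitoring figure and the sample-size table come from different formulas (the table implies about 93), and the pooled 92% power is not net of the protocol's own 10% allowance

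*Protocol*

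**What the plan says.** Everything here is in the Protocol, under Sample size calculations and statistical analysis.

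- **Method stated for the table:** "Calculations are performed for a chi-squared test comparing two proportions", at 5% significance and 80% power. Sidedness is not stated.
- **Chosen cell:** 24% control risk and hazard ratio 0.55, giving 245 per group and 490 in total.
- **Allowance:** "We have increased the number by 10% to take account any" cross-overs or losses to follow-up not due to stroke. 490 × 1.10 = 539, stated as 540.
- **Pooled analysis with VAST:** VAST's 180 patients are added to the 540. "Therefore the combined sample size will be 720 (360 per treatment arm"). The power is given as 92%, introduced by "With the same assumptions we made above", with a bracket that reads "average event rate 24%, treatment effect is a hazard ratio of 0.55".
- **Monitoring:** the section says that, for a given hazard ratio, what matters is the total number of events. "For a hazard ratio of 0.55 this number is 88 events". The steering committee is to follow accumulating events and discuss a larger sample or longer follow-up. No formula is named for the 88.

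**The concern.** The table and the event count appear a few lines apart, for the same hazard ratio, significance level and power, so they should agree. They do not. The committee would be judging progress against a number slightly lower than the one the sample size was built to deliver.

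The pooled power raises a related point. For VIST alone, 490 patients give 80% power and the extra 50 are there to absorb cross-overs and losses. In the pooled calculation those 50 count as full contributors. The 80% and the 92% are therefore not on the same footing, and the second looks more favourable than it should beside the first.

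**Working it through.** **Inputs.** α = 0.05, taken as two-sided (an assumption; it reproduces the table); power 80%; control risk p₁ = 0.24 as stated; hazard ratio 0.55. Under proportional hazards the stented-arm risk is p₂ = 1 − 0.76^0.55 = 0.1401, so p₁ + p₂ = 0.3801. (1.960 + 0.842)² = 7.849.

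**1. Reproducing the table**

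- Freedman: events = 7.849 × [(1 + 0.55)/(1 − 0.55)]² = 93.12. Per group: 93.12/0.3801 = 244.99, rounded up to 245, as printed.
- The same formula, rounded up, matches all 18 printed cells. The closest call is 28% with hazard ratio 0.40, which computes to 106.001 and rounds up to the printed 107.
- Uncorrected chi-squared, with p̄ = 0.190: [1.960√(2p̄(1 − p̄)) + 0.842√(p₁(1 − p₁) + p₂(1 − p₂))]²/(p₁ − p₂)² = 240.9, so 241. It falls below the printed value in every cell. With continuity correction the chosen cell is 261.

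**2. Reproducing the 88**

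- Schoenfeld: 4 × 7.849/(ln 0.55)² = 87.84, rounded up to 88.
- Events implied by the chosen cell: 245 × 0.3801 = 93.1.
- On Schoenfeld's basis the cell would have been 87.84/0.3801 = 231.1, so 232 per group rather than 245.

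**3. Power at 88 events**

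- Schoenfeld: Φ(½√88 × 0.598 − 1.960) = 80.1%.
- Freedman: Φ(√88 × 0.45/1.55 − 1.960) = 77.7%.
- Simulated log-rank test at the 88th event (hazard ratio 0.55, 20,000 runs each): 78.6%, 78.8% and 79.9% with 245, 270 and 360 per group.
- With 94 events: Freedman 80.4%, Schoenfeld 82.6%, simulation about 82–83%.

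**4. Pooled power**

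| Per arm | Basis | Freedman | Chi-squared | Schoenfeld |
|---|---|---|---|---|
| 360 | all 720 counted | 92.4–92.5% | 92.9% | 93.8% |
| 335 | (490 + 180)/2: allowance off VIST only | 90.6% | 91.1% | 92.1% |
| 324 | 0.9 × 360: allowance off both | 89.7% | 90.2% | 91.3% |

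Freedman with 360 per arm uses 360 × 0.3801 = 136.8 events and reproduces the stated 92%. Dividing by 1.10 instead of multiplying by 0.9 in the last row gives 327 per arm, with 89.9% (Freedman) and 90.4% (chi-squared).

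**The case against.** **88 is a legitimate number.** Schoenfeld's formula is standard and gives 80.1% in its own terms. The simulation puts the true power about one point or less below 80%, and 94 events overshoot 80% slightly. This stands: the fault is inconsistency with the table, not a wrong calculation.

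**A reader might infer that 88 leaves out the loss-to-follow-up allowance.** It does not. Loss to follow-up changes how many patients must be recruited to see a given number of events, not how many events are needed. Only cross-overs could raise the count, by pulling the intention-to-treat hazard ratio towards 1. The protocol does not divide its 10% between cross-overs and losses, so any specific higher target would rest on an invented share.

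**A reader might infer that the trial would stop at 88 and end under-powered.** No such rule exists. The committee monitors and discusses; follow-up runs from 2 to about 8 years; and a data monitoring committee review of conditional power is planned. On the protocol's own three-year risks, 540 fully followed patients would give 270 × 0.3801 = 103 events, already above either figure.

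**The pooled 92% is correct for what it describes.** The bracket that spells out the shared assumptions lists only event rate and hazard ratio, so there is no flat contradiction. If Schoenfeld's formula were used throughout, 335 per arm would still give 92.1%. However, the text ties the 92% to 720 patients, and Schoenfeld's formula is not the one behind the 245. What remains is that, on the table's basis or the stated chi-squared basis, the 92% is a figure with no attrition and no cross-over.

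**Conclusion.** The point holds as a modest internal inconsistency.

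- The table is a Freedman log-rank calculation labelled as chi-squared (245 against 241 per group for the chosen cell).
- The monitoring figure is 5 to 6 events, about 6%, below what the table implies. At 88 events power is about 78–80%, depending on the approximation.
- Pooled power net of the protocol's own allowance is about 90.6–91.1% if the allowance is removed from VIST only, and about 90% if it is removed from both trials. That is roughly 1 to 2.5 points below the stated 92%. Which case applies is open, because the protocol does not say whether VAST's 180 already includes an allowance.

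These results assume a two-sided test, proportional hazards and the stated 24% control risk. Whether the yearly risks listed in the same section (12%, 6% and 4%) support 24% is a separate question. It is not used here to lower the pooled power further.

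**What to change.** In the sample-size section of the protocol:

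1. Describe the table as a log-rank calculation by Freedman's formula, in place of the chi-squared description.
2. Replace 88 by 93–94 events (93.1, or 94 rounded up), so that the monitoring target matches the table. If 88 is kept, name Schoenfeld's formula and explain the difference from the table.
3. State that the target assumes an undiluted hazard ratio of 0.55, and that cross-overs would raise it.
4. Restate pooled power as about 90–91% after the allowance, and say whether VAST's 180 includes one.

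The cost is a change of wording, an event target reached slightly later, and a slightly lower stated pooled power. No patients are added; the planned 540 would be expected to exceed 94 events on the protocol's own rates with full follow-up.
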